**DEFINITIONS OF ACRONYMS:**

BMQ = Brief Medication Questionnaire  
CBT = cognitive-behavior therapy  
DSM-5 = Diagnostic and Statistical Manual of Mental Disorders  
HLM = hierarchical linear models  
IPIP = International Personality Item Pool  
MBSR = mindfulness-based stress reduction  
PCL-5 = PTSD Checklist for DSM-5 with Life Events Checklist  
PFDI-20 = Pelvic Floor Distress Inventory  
PGI-I = Patient Global Impression of Improvement  
PROMIS = Patient Reported Outcomes Measurement Information System  
PTSD = posttraumatic stress disorder  
RRS = Ruminative Responses Scale  
UDI-6 = Urinary Distress Inventory  
UP-CBT = Unified Protocol Cognitive-Behavior Therapy

## **1.0 Purpose of the study:**

### **1.1 Purpose**

The purpose of this proposal is to test a novel behavioral treatment – Unified Protocol Cognitive-Behavior Therapy (UP-CBT) – to enhance quality of life in women with pelvic floor disorders. Emotional distress is treatable using behavioral procedures, and effective treatment would increase women’s emotional health and help to reduce urinary symptoms (e.g., incontinence, frequent urination). Women with pelvic floor disorders are often seen in the urogynecology or urology clinic, which makes this setting ideal for offering additional interventions that may improve their quality of life. Unfortunately, many women with pelvic floor disorders may not receive effective behavioral treatment, such as cognitive behavior therapy, because urogynecologists, urologists, and other medical professionals may not be aware of providers in their community who offer this treatment. We will enhance treatment options by 1) providing evidence for an all-purpose cognitive-behavioral intervention (i.e., UP-CBT), 2) offering and integrating treatment in the medical clinic, maximizing convenience, and 3) improving clinical outcomes for these patients.

### **1.2 Specific Aims**

1. To demonstrate that UP-CBT is an effective form of therapy for women with lower urinary tract symptoms.
2. To use baseline characteristics in moderation analyses to determine which women will be most likely to have a good response to therapy.
3. To use mediation analyses to test a possible causal chain of events – Does treatment lead to lower anxiety, which in turn leads to fewer urinary symptoms?

### **1.3 Hypotheses**

1. We hypothesize that UP-CBT will reduce anxiety, and urinary symptoms in women suffering from lower urinary tract symptoms, at post treatment and follow-up.
2. UP-CBT will be compared to a control condition, supportive therapy. Supportive therapy, although often used in clinical settings (e.g., in support groups), is not expected to reduce anxiety, or urinary symptoms on average. Thus, we expect that the benefits of UP-CBT will be greater than benefits of the control therapy, supportive listening.

## **2.0 Background / Literature Review / Rationale for the study:**

### **2.1 Gaps in Current Knowledge**

Urinary symptoms are common health issues affecting an individual’s quality of life, including mental health. Urinary symptoms include urgency, frequency, incontinence, nocturia, and overactive bladder. We propose a novel behavioral intervention to improve quality of life in women suffering from urinary symptoms. Many women suffer from urinary symptoms, and these symptoms often cause emotional distress as anxiety and depression are both risk factors for developing urinary symptoms. Similarly, urinary symptoms can be exacerbated by emotional distress. Urinary symptoms and pelvic floor disorders affect nearly one in four women. Women with incontinence are both more likely

to have baseline emotional distress and to develop emotional distress as a result of their incontinence. Yet, current methods to treat incontinence do not address the emotional impact that urinary symptoms may have on women. In fact, one in five women will have surgery for these disorders with 30% needing a second surgery for the same condition. Therefore, more research is desperately needed on non-surgical treatments for these problems that affect millions of women.

## **2.2 Background**

This study addresses how treatment of overall emotional distress affects anxiety, and in turn urinary symptoms. By experimentally manipulating the trajectory of anxiety through treatment, this study will also give insight into emotional distress as a mechanism of urinary symptoms. Although there is a strong connection between emotional distress and urinary symptoms, evidence on their causal connections remain unexplored. Furthermore, research on cognitive-behavior therapy (CBT) for people with urinary symptoms is lacking. Our study will be the first to apply an empirically-supported, transdiagnostic cognitive- and behaviorally-based treatment to women suffering from urinary symptoms, carried out in accord with high quality psychotherapy trials. The existing evidence base is limited to mindfulness-based stress reduction (MBSR) and physical therapy techniques (e.g., pelvic floor exercises) as treatments for urinary symptoms, which did not address co-occurring symptoms of emotional distress.

Cognitive-behavior therapy has a well-developed protocol and thus can be administered to women of all ages, and of all economic backgrounds. The intervention is time-limited and low-cost, requiring only visits with the behavior therapist and a low-cost workbook that is widely available. This project will also facilitate systemic change by bringing a behavioral intervention directly to the woman, as opposed to asking the patient to schedule appointments in a different location. Delivering cognitive-behavior therapy in the medical setting, such as in primary care, has been used successfully in previous studies, but currently does not exist at Northwestern Medicine. This study can also bring systematic change to the practice of medicine by advancing another possible treatment (i.e., UP-CBT) at the disposal of doctors who are treating women with pelvic floor disorders.

## **3.0 Inclusion and Exclusion Criteria:**

### **3.1 Criteria**

Women must be 18 years of age or older to participate. They must have one or more urinary symptoms, including frequency, nocturia, urgency, leakage, hesitancy, straining, or dribbling. Women who present with clinical signs of anxiety based on the physician exam, have any documented anxiety disorder in the medical record and/or are taking medication for anxiety will be eligible for the study. Women must consent to randomization to treatment, and be willing to complete 12 sessions of treatment, as well as to complete baseline and outcome questionnaires. Women that screen positively for an alcohol or substance use disorder (based on the medical record) will be excluded from the study. Any women with blood in the urine, a positive urine culture, or other signs of possible infection will be deferred until they have been evaluated and treated as needed. Women who are pregnant or who have given birth within the past 6 months will be

excluded from the study. Other exclusion criteria include serious disease that would impede participation (e.g., Alzheimer's dementia, Parkinson's disease); recent (within 6 months) pelvic or endoscopic surgery, urethral stricture, pelvic malignancy, current chemotherapy or other cancer therapy, pelvic device or implant complication; recent (within 12 months) Botox injection to the bladder or pelvic structures; or difficulties communicating in English. Women who are currently in their own psychotherapy are ineligible for the study.

In addition, participants must be willing to defer from usual treatment for urinary problems until after completing the 12-week therapy intervention. For these women with lower urinary tract symptoms, there are multiple treatment options that can be tried sequentially, including the management of anxiety. Thus, if the person consents to be in the study, they will agree to these procedures before trying an alternative management strategy. Some alternatives include physical therapy (e.g., pelvic floor therapy), which can be uncomfortable and/or painful, or even surgery, which has other complications. Thus, psychotherapy is a reasonable and viable alternative. Lower urinary tract symptoms are not life threatening, so waiting to start an alternate therapy will cause waiting for the participant, but no harm. The participant will of course have the choice not to agree to the study and pursue other treatments, or no treatment, if they wish. If a patient is eligible, they will then be given the opportunity to provide informed consent.

Table 1. Summary of Inclusion and Exclusion Criteria

Inclusion Criteria	Exclusion Criteria

 
1. Female
 
2. Age 18 years or older
 
3. Presence of one or more of the following urinary symptoms in past 12 months and currently seeking treatment: frequency, nocturia, urgency, leakage, hesitancy, straining, or dribbling
 
4. Willing and able to provide informed consent
 
5. Anxious presentation and/or history of anxiety
 
6. English speaking
 
7. Willing to defer usual treatment for urinary problems
 
	
 
1. Blood in the urine, positive urine culture, signs of infection
 
2. Pregnant, or 6 months or less postpartum
 
3. Psychosis, dementia, or other cognitive impairment that would preclude participation
 
4. Recent (within 6 months) pelvic or endoscopic surgery, urethral stricture, pelvic malignancy, current chemotherapy or other cancer therapy, pelvic device or implant complication
 
5. Recent (within 12 months) Botox injection to the bladder or pelvic structures
 
6. Currently in psychotherapy
 
7. Current alcohol or substance use disorder
 
8. Difficulty communicating in English
 

### 3.2 Special populations

This study will not include any special populations.

#### **4.0 Sample Size:**

This study will include up to 40 participants. UP-CBT has been shown to have quite large effects (Cohen's  $d$  values of 1.7 or greater). For this study, we have chosen a slightly more conservative estimate for Cohen's  $d$  of 1.5, which represents 1.5 standard deviations between the treatment effect of UP-CBT versus the control group. Based on a power analysis, we would require 16 women per group, in the data analyzed, to detect a treatment effect with  $> 98\%$  power with a Type I error rate of  $\alpha = .05$ , two-tailed. Study withdrawal is estimated at roughly 20%, leaving an estimated final sample of 32 participants for data analysis (see CONSORT diagram below).

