### 8.5 Analysis Plan

**Primary analyses.** We will create hierarchical linear models (HLM) to test the primary hypotheses of the study. One model will determine the effect of type of therapy on anxiety. A separate model will determine the effect of type of therapy on urinary symptoms. The dependent variables for these models will be the UDI-6 subscale of the PFDI-20 and anxiety as measured by the anxiety subscale of the PROMIS Profile-29. The structure of the HLM model is shown below. Note that these models create a response profile for each person across all time points as described in the protocol.

#### Level 1

$$Y = P_0 + P_1(T_2) + P_2(T_3) + P_3(T_4) + P_4(T_5) + E$$

#### Level 2

$$P_0 = B_{00} + B_{01}(\text{Condition})$$

$$P_1 = B_{10} + B_{11}(\text{Condition}) + R_1$$

$$P_2 = B_{20} + B_{21}(\text{Condition}) + R_2$$

$$P_3 = B_{30} + B_{31}(\text{Condition}) + R_3$$

$$P_4 = B_{40} + B_{41}(\text{Condition}) + R_4$$

The dummy variables P1-P4 are dummy codes for the five time points. These will allow us to determine the degree of change from baseline. Each of the "P" coefficients is influenced by Level-2 variables. T2 - T5 are dummy variables of the time differences from baseline. E, R1-R4 represent error terms in the model. Condition will be dummy coded (UP-CBT = 1, Supportive Therapy = 0).

**Testing Key endpoints.** We have two primary endpoints and therefore we will have two models. For both anxiety (PROMIS T score) and urinary symptoms (UDI-6), the full model (see above) will be compared to a reduced model with all of the terms involving condition removed (i.e., B01, B11, B21, B31, and B41). If this comparison is significant ( $p < .05$ ), then we will test individual parameters at a Type I error rate of alpha = .05 (two-tailed). Note, these tests will only be carried out if the full-reduced model comparison is

significant. The key prediction for anxiety is that parameters B21, B31, and B41 (representing the effect of UP-CBT at post-treatment and beyond) will be significant and negative (representing fewer symptoms). The key prediction for urinary symptoms is that parameters B21, B31, and B41 (representing the effect of UP-CBT at post-treatment and beyond) will be significant and negative (representing fewer symptoms).

**Missing data.** All participants with baseline data will be included in the modeling using an intent-to-treat approach. The HLM approach described above can accommodate cases with missing follow-up data.

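### The >98% power in section 4.0 is right for one two-group comparison at d = 1.5, but it is not the power of the section 8.5 procedure, and less so with the covariance as printed

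*Combined protocol and SAP*

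**What the plan says.** Section 4.0 gives the only power statement in the plan: "we would require 16 women per group, in the data analyzed, to detect a treatment effect", at d = 1.5, two-tailed alpha .05, power above 98%. It glosses d as a value "which represents 1.5 standard deviations between the treatment effect of UP-CBT versus the control group". It does not name the outcome, the assessment, the test, or whether the SD is that of the raw score or of the change score. With about 20% withdrawal, 40 enrolled give 32 analysed.

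Section 8.5 (Primary analyses) fits a five-occasion hierarchical model to each of two primary endpoints, PROMIS anxiety and UDI-6, with dummy codes for the four post-baseline assessments. Of these codes it says: "These will allow us to determine the degree of change from baseline". The P0 equation has no random term, and the text agrees: "E, R1-R4 represent error terms in the model".

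Under Testing Key endpoints, five condition terms are first tested together in a full-versus-reduced comparison, and single parameters come second: "Note, these tests will only be carried out if the full-reduced model comparison is" significant. Then: "The key prediction for anxiety is that parameters B21, B31, and B41" will be significant with a negative sign, and likewise "The key prediction for urinary symptoms is that parameters B21, B31, and B41". Under Missing data: "All participants with baseline data will be included in the modeling using an intent-to-treat approach".

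**The concern.** The power in section 4.0 belongs to one test. The prediction in section 8.5 concerns three tests per endpoint behind a gate, and no power is given for that sequence. Two features lower it at the plan's own d = 1.5:

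- Three parameters are predicted, not one.
- Without R0, and with independent E, the printed model makes baseline uncorrelated with every later visit. If visits are positively correlated, its standard errors for change from baseline are too large.

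At stake is how the result is read. Someone who takes >98% as the chance of confirming the prediction would treat a partly negative result as strong evidence against UP-CBT. The margin also shrinks quickly below d = 1.5. At d = 1.0 on the change scale one t-test has 78% power, while gate plus all three has about 55-58% even with an unstructured covariance. Section 4.0 derives d = 1.5 from effects attributed to UP-CBT in general and gives no value for UDI-6, which section 8.3 names as the primary outcome tool.

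**Working it through.** **Inputs from the documents.** 16 analysed per arm, d = 1.5, two-sided alpha .05, 20% withdrawal and up to 40 enrolled (section 4.0); five assessments (section 8.3); gate on B01, B11, B21, B31 and B41, then B21, B31 and B41, with error terms E and R1-R4 (section 8.5).

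**Assumptions, not in the documents.** Unit variance and compound symmetry with within-person correlation ρ = .3/.5/.7; complete data; the same effect at post-treatment, 3 and 6 months; half of it at session 6.

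**Step 1: the plan's figure.** Noncentrality = 1.5 × √(16/2) = 4.243 on 30 df gives power 98.4%. With 15 per arm it is 97.7%, so 16 is the smallest n above 98%. 32/(1 − 0.20) = 40. Section 4.0 is arithmetically right.

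**Step 2: the scale of d.** The SD of change is √(2(1 − ρ)).

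- A raw d of 1.5 becomes 1.5/√(2(1 − ρ)) = 1.27/1.50/1.94 on the change scale.
- A change d of 1.5 is a raw difference of 1.5 × √(2(1 − ρ)) = 1.77/1.50/1.16 SDs.

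The two readings therefore move in opposite directions as ρ rises.

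**Step 3: what the missing R0 does.** The printed model sets the baseline variance to σ², the baseline-to-later covariance to 0, and the later-visit covariance to Tau + σ²I. No eigenvalue of the later-visit block can then be below σ². The true block has eigenvalues 1 + 3ρ (once) and 1 − ρ (three times). In large samples the fit pools the three small ones with the baseline variance:

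- σ² = [1 + 3(1 − ρ)]/4 = .775/.625/.475
- later variance = [(1 + 3ρ) + 3σ²]/4 = 1.056/1.094/1.131
- model variance of change = their sum = 1.831/1.719/1.606
- true variance of change = 2(1 − ρ) = 1.4/1.0/0.6
- standard error too large by √(1.831/1.4) = 1.14, √(1.719/1.0) = 1.31, √(1.606/0.6) = 1.64

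In simulation with no true effect, the B21 test (before the gate) rejects 2.5%/1.0%/0.2% of the time instead of 5%.

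**Step 4: power of the section 8.5 sequence.** 40,000 simulated trials per setting, one endpoint, 16 per arm, d = 1.5. Gate: ML likelihood ratio on 5 df. Parameters: REML standard errors, t on 30 df, significant and negative. Entries are percentages at ρ = .3/.5/.7.

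| Rule and covariance | d in change SDs | d in raw SDs |
|---|---|---|
| Gate + B21, B31, B41; unstructured | 95.8/95.8/95.9 | 84.7/95.6/99.9 |
| Gate + B21; unstructured | 98.3/98.4/98.3 | 93.5/98.4/>99.9 |
| Gate + B21, B31, B41; as printed | 93.2/86.1/58.8 | 77.9/85.9/94.3 |
| Gate + B21; as printed | 97.3/93.6/72.9 | 89.8/93.7/97.2 |

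The printed rows let R1-R4 correlate freely, which section 8.5 does not specify. With R1-R4 independent, the three-parameter row is 92/82/50 (change) or 75/82/90 (raw). With ML standard errors and normal critical values, the printed three-parameter row on change is 95.4/89.8/66.0, and gate plus B21 is 98.2/95.2/76.6.

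With the unstructured covariance on change, the gate itself costs almost nothing at d = 1.5 (passed in at least 99.5% of trials). The loss there comes from asking for three parameters.

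**Step 5: effect detectable with 80% power, 16 per arm.** Single test: d = 1.02. Gate plus all three, unstructured: d = 1.21/1.21/1.22 on change, or 1.43/1.21/.94 in raw SDs.

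**The case against.** Section 4.0 speaks of one treatment effect, and for one effect its figure is right. Gate plus B21 on change with an unstructured covariance also gives 98%, so the figure matches a planned parameter. This stands, and it is why the remedy allows B21 to be named as the powered parameter.

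A reader might infer that the trial fails unless all three parameters are significant. The documents do not say so. Section 8.5 tests parameters individually after the gate and states a prediction about three of them; it sets no all-or-nothing rule. The 96% is therefore the power of the stated prediction, not the probability of a successful trial.

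A reader might also take 59% as the trial's power. That is not supported either. It belongs to one reading of d and one assumed correlation, under a covariance that should not be fitted. On the change scale, part of the fall comes from holding d at 1.5 while the raw difference shrinks from 1.77 to 1.16 SDs. In raw SDs the same model's power rises with correlation, from 78% to 94%.

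The missing R0 may be a slip in the equations. But it is absent from both the P0 equation and the sentence listing the error terms, so the text as it stands has to be corrected.

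Finally, section 8.5 models everyone with baseline data. If all 40 were complete (20 per arm), gate plus all three with an unstructured covariance would reach 99% on change, or 93%/99%/>99.9% in raw SDs. So 16 per arm is the cautious end. Section 8.1 also calls the study a pilot, which limits the consequences.

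**Conclusion.** The point holds in a limited form. The >98% is correct for one two-group comparison at d = 1.5 and should not be read as the power of the section 8.5 procedure. With a sound covariance the shortfall for the three-parameter prediction is about 2 points on change (96% against 98%). In raw SDs it ranges from about 14 points at correlation .3 (85%) to none at .7 (99.9%).

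With the model as printed, even gate plus B21 stays below 98% on either scale at all three correlations when REML standard errors and 30 df are used. With ML standard errors and normal critical values, one setting (change, correlation .3) just reaches it. The larger losses come from the covariance, not from the number enrolled, so they are a matter for section 8.5.

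The direction is secure. The sizes rest on the assumed correlations, compound symmetry, complete data and a sustained equal effect. Nothing here shows that section 4.0's arithmetic is wrong or that enrolment must change.

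**What to change.** 1. **Section 8.5:** add R0, correlated with R1-R4, or fit an unstructured covariance, so that the model uses the baseline-to-later correlation. Unstructured is the simpler choice: five visits have 5 × 6/2 = 15 variances and covariances, and a full R0-R4 matrix plus E has 16 parameters, so E would not be separately identified.
2. **Section 4.0:** label >98% as the power of a single two-group comparison with 16 per arm, and state the outcome, assessment and SD type (raw or change) to which d = 1.5 refers.
3. **Section 4.0:** either name B21 as the powered parameter, or give power for the three-parameter prediction under the corrected covariance, as a range over stated correlations: about 96% on change, or 85% to 99.9% in raw SDs. Do not quote >98% for that prediction, and do not enter 93%/86%/59% as the trial's power; those figures only show why the printed covariance needs correcting.
4. **Section 4.0:** state that no UDI-6-specific effect size is given, and report the effect detectable with 80% power: d = 1.02 for a single test, and about 1.21-1.22 on change for the three-parameter prediction with an unstructured covariance.

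The cost is some rewording, one corrected model statement and a short simulation. Enrolment does not change. The downside is a slightly less favourable stated power, and a within-person correlation that the team must assume and state.

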#### **5.0 Research Locations:**

Participant recruitment and consent will occur at the Northwestern Medicine Integrated Pelvic Health Program (IPHP) clinic within the Department of Obstetrics and Gynecology and through the Northwestern Medicine Urology clinic. [name] will oversee recruitment at the IPHP and [name] will oversee recruitment at the urology clinic. Use of IPHP space has been approved by [name], the chief of Urogynecology. Therapist training will take place in the [name] lab space in the Department of Medical Social Sciences (MSS). [name] has approved use of this space for this research project. Therapy sessions will take place in the [name] lab space in MSS and in the IPHP clinic space in the Arkes Pavilion of Northwestern Memorial Hospital. Data will be stored at the [name] lab space, and specific secure cabinets have been designated for this study.

#### **6.0 Multiple sites:**

NA

#### **7.0 Reliance Agreements/Single IRB:**

NA

#### **8.0 Procedures Involved:**

##### **8.1 Randomization and Study Design**

This is a pilot study to test pre-post changes associated with UP-CBT, urinary symptoms, and emotional distress. Women eligible for the study will be randomized to treatment based on a predetermined list created using the `blockrand` package of R. Randomization will occur by blocks, with varying block sizes, in accord with recommended methods for RCTs. The randomization key will be linked to a unique study ID number, as well as to a treatment condition (UP-CBT or Supportive Therapy).

[figure not shown]

Figure 1. Study Design CONSORT Flow Diagram

